10.0 Statistical Considerations

We will test the hypothesis that (*R*)-propafenone is superior to (*S*)-propafenone and (*S*)-propafenone is superior to (P)-placebo at suppressing AF in patients undergoing an AF ablation. Our primary analysis will use multivariable regression to test whether our primary determinant (*R*-propafenone versus *S*-propafenone) and (*S*-propafenone versus placebo) significantly reduces the primary endpoint of inducibility of AF after study drug infusion (yes/no). Inducibility of AF will expressed as an ordinal variable based on the stage of the induction protocol that AF was induced (Stage 0, Stage 1, Stage 2). Patients who had only AFL induced will not be included in the primary analysis, but will be included in a secondary analysis. Adjustment will be made for age, sex, and other established AF risk factors. To avoid over-fitting of multivariable regression, a 10:1 ratio for degrees of freedom per the less frequent outcome event will be used in our modeling. The sample size of 243 (108 for *R*-propafenone, 108 for *S*-propafenone, and 27 for placebo), was selected to power an exploratory pharmacogenomics aims that analyzes common variants at the 4q25 AF risk allele. A blinded interim analysis reviewed by the DSMB in March 2019, demonstrated a difference was emerging between the treatment groups for the new primary ordinal endpoint with a P-value of 0.075, thus continued enrollment was recommended.

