2.0 Rationale and Specific Aims

The overarching aim of our study is to test the hypothesis that RyR2 blockade is beneficial for preventing AF induction in humans with paroxysmal AF. We have received an NIH R01 award to evaluate the efficacy of RyR2 channel blockade to prevent inducible AF or atrial flutter (AFL) in patients undergoing an AF ablation. We will test the role of *RyR2* channel blockade by comparing drugs with variable *RyR2* action: (*R*)-propafenone, (a combined RyR2 and Na channel blocker), and (*S*)-propafenone (largely devoid of *RyR2* inhibition).

Specific Aim: To test the hypothesis that (*R*)-propafenone is superior to (*S*)-propafenone in suppressing induction of AF/AFL by a rapid atrial pacing protocol.

Rationale: Recent human studies have shown that paroxysmal forms of AF are associated with increased Ca leak from intracellular Ca stores and RyR2 dysfunction. But, it remains controversial if this abnormal Ca leakiness is mechanistically important for AF risk in humans. In mice, enhanced diastolic Ca release mediated by loss of the Ca-binding protein Casq2 can cause AF by promoting regional Ca elevations and DADs. Furthermore, inhibition of spontaneous Ca release with (*R*)-propafenone prevented AF by reducing the rate of DADs and triggered atrial activity, whereas Na channel blockers without RyR2 blocking properties (S-propafenone and lidocaine) were much less effective. These data suggest that RyR2 blocking properties are important for therapeutic efficacy against AF caused by leaky RyR2. The general approach for this study will utilize a rapid atrial pacing protocol to induce AF in subjects undergoing AF ablation. Subjects referred for AF ablation will be randomized to either (*R*)-propafenone, (*S*)-propafenone, or placebo (vehicle) in a double blind, randomized fashion. A single 10-minute infusion of intravenous (*R*)- or (*S*)-propafenone or placebo (vehicle) will be given at the start of the ablation procedure before a rapid atrial pacing protocol is performed to test inducibility of AF.

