 - Some patients will develop AF/AFL during the standard clinical EP study. If it sustains >30 seconds it will be counted toward the primary endpoint, and the research AF induction pacing protocol will not be performed.
 - Standard-of-care monitoring following an AF ablation is inpatient 23-hour continuous cardiac telemetry observation with specialized cardiac-trained nursing care. Cardiac-trained nurse practioners remain in the hospital overnight and communicate with the electrophysiology fellow on call at night for any patient care issues. Intravenous access is maintained post-procedure during their hospitalization.

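### Section 10 puts two contrasts in the primary analysis with no order or success rule, and its primary endpoint is inconsistent within section 10 and with sections 2 and 6

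*Combined protocol and SAP*

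**What the plan says.** **Contrasts.** Section 10 states two superiority hypotheses joined by 'and': R over S, and S over placebo. The primary analysis is a multivariable regression "to test whether our primary determinant", followed by R v S and then by S "versus placebo) significantly reduces the primary endpoint of inducibility of AF after study drug infusion (yes/no"). No alpha, sidedness, order or success rule is given. Section 2 has one Specific Aim, which is R v S.

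**Endpoint.** Section 10 calls the endpoint yes/no and in the next sentence makes it ordinal (Stage 0, 1, 2). It adds: "Patients who had only AFL induced will not be included in the primary analysis". The aim in section 2 is superiority "in suppressing induction of AF/AFL by a rapid atrial pacing protocol". Section 6 says of AF/AFL arising in the clinical EP study: "If it sustains >30 seconds it will be counted toward the primary endpoint". Section 9, item iv, lets the PI withdraw a patient who goes into AF, atrial tachycardia or flutter spontaneously before the study protocol is complete.

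**Interim look.** "A blinded interim analysis reviewed by the DSMB in March 2019" is said to have "demonstrated a difference was emerging between the treatment groups for the new primary ordinal endpoint with a P-value of 0.075"; "thus continued enrollment was recommended".

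**The concern.** A reader of the final report must know which result counts as success. Section 10 fits three rules: R v S decides (alone or first), both contrasts must succeed, or either is enough. They carry different error rates.

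The endpoint conflict changes who is analysed. Whether a patient has only AFL is known after randomisation and may depend on the drug, so dropping such patients can unbalance the arms being compared.

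The description of the look leaves open who knew what when the primary endpoint became the new ordinal one, and so whether the final P can be read at face value.

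**Working it through.** **1. The plan's own figure.** 108 + 108 + 27 = 243, as stated. Section 10 says this size was chosen for an exploratory pharmacogenomic aim. It gives no alpha, power or effect for either primary contrast, so there is no stated error rate to reproduce.

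**2. Inputs.** Arm sizes are from section 10. Assumed: two-sided 0.05 per contrast (critical value 1.96), equal variance per patient, normal test statistics, final analysis only.

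**3. Correlation of the contrasts, which share the S arm.**
- Variance of R v S is proportional to 1/108 + 1/108 = 0.01852.
- Variance of S v placebo is proportional to 1/108 + 1/27 = 0.04630.
- Correlation = -(1/108) / sqrt(0.01852 × 0.04630) = -0.316.

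**4. Familywise error (bivariate normal).**

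| Success rule | Any significant result, either direction | False claim of benefit only |
|---|---|---|
| R v S sole or first | 5.0% | 2.5% for R v S alone |
| Both must succeed | 0.5% under the global null; at most 5% otherwise | 0.006% under the global null |
| Either suffices | 9.5% | 5.0% |

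The hypotheses are directional, so the last column is nearer to what a false success would mean. On either basis, either-suffices roughly doubles the single-contrast rate. Section 5 speaks of arms in balance after each block; with equal arms (correlation -0.5) the 9.5% becomes 9.1%.

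**5. Cost of ordering the tests.** The standard error of S v placebo is sqrt(0.04630/0.01852) = 1.58 times that of R v S. Suppose R v S has 80% power (mean statistic 1.96 + 0.84 = 2.80) and the S v placebo effect is equally large. Its mean statistic is then 2.80/1.58 = 1.77.
- Tested alone, S v placebo has 43% power.
- In sequence, both contrasts succeed with probability 30%.
- R v S stays at 80% in sequence. An equal split at 0.025 each would cut it to 71%.

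**6. Endpoint.** Take a patient whose AFL lasts 40 seconds during the clinical EP study, with no AF. Section 6 counts this toward the primary endpoint and omits the pacing protocol. Section 10 leaves the patient out of the primary analysis. If the onset is judged spontaneous, section 9 item iv also allows withdrawal. These rules cannot all be followed.

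Two coding gaps remain. Stages 0/1/2 are not mapped to Steps 1 and 2 of section 6, and AF sustained in the EP study, before either step, has no level. If Stage 0 means never induced, the numerical order 0, 1, 2 is not the order of ease of induction, which would run 1, 2, 0, because Step 2 is used only when Step 1 fails.

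**7. The look.** Reported: date, DSMB review, ordinal endpoint, P = 0.075, recommendation to continue. Not reported: which comparison, the information fraction, any decision rule, what blinded meant beside a between-group P, and when and why the endpoint changed. If no success claim was possible at the look and the endpoint was not chosen on unblinded results, it adds nothing to the figures in step 4.

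**The case against.** The strongest reply is that the text already points to R v S. The determinant is singular and is followed first by R v S, the Specific Aim names only that contrast, and the hypotheses are joined by 'and'. On the readings closest to the text, the contrasts alone cost at most 5%. Section 1 also calls this a proof-of-concept trial, where strict familywise control is a matter of judgement. This largely stands: 9.5% is the least supported case, not the expected one. It does not supply the missing rule, since both contrasts are written into the primary analysis.

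On the endpoint, it is fair to say that it is defined. Section 6 gives a 30-second criterion, and the later mention of an ordinal primary endpoint suggests that yes/no is leftover wording. That stands for yes/no. It does not resolve the AFL conflict or the stage coding.

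On the look, a reader might infer that the trial took an unadjusted look for success, or that the ordinal endpoint was picked because it performed better. The documents support neither inference. P was 0.075, enrolment continued, and no success claim is reported. For scale only: one contrast tested at an unadjusted 0.05 at both an assumed half information and the end would carry 8.3%, but no such stopping rule is documented.

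**Conclusion.** The point holds in three parts of unequal weight.

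- **Contrasts:** the missing order and success rule is a real gap. Its effect runs from none (R v S sole or first) to 9.5% in the least supported reading. These figures rest on an assumed two-sided 0.05 and the final analysis alone, so they are not bounds on the whole trial's error.
- **Endpoint:** this is a contradiction, not just missing detail. Sections 6 and 10 give different primary analysis sets, and the section 10 rule excludes patients on a post-randomisation outcome. The documents give no AFL frequency, so the size of the effect cannot be computed. It would be wrong to call the endpoint undefined; it is inconsistent and incompletely coded.
- **Look:** mainly a matter of disclosure. It adds type I error only if it could have led to a success claim or if the endpoint was chosen on unblinded results. The documents neither show nor exclude either.

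**What to change.** 1. State alpha as 0.05 two-sided. Test R v S first at full alpha, and S v placebo only if R v S is significant. Disclose it if anyone choosing this order had already seen between-group results.
2. Name the ordinal endpoint as the single primary and delete the yes/no wording. Map the stages to Steps 1 and 2, and assign a level to AF/AFL sustained during the EP study. Apply one AFL rule in sections 2, 6, 9 and 10 that keeps every randomised patient with an inducibility result in the primary analysis, with AFL-only patients in a defined category. Reconcile section 9 item iv with section 6. Report the yes/no AF/AFL result in all patients beside the primary result.
3. State when and why the endpoint changed, who saw the March 2019 P value and, if true, that the look allowed no efficacy claim. If the endpoint was chosen on unblinded results, or an efficacy claim was possible without a strict limit, report the final P as nominal.

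**Cost.** Protocol and SAP wording and one supporting analysis. S v placebo cannot be claimed if R v S fails; in the example its chance of being claimed falls from 43% to 30%, while R v S keeps its power. If the look or the endpoint change cannot be cleared, the final P loses its confirmatory standing.

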1C. Are "leaky" RyR2 channels a common downstream consequence of genetic AF risk variants? Recent insight into underlying AF mechanisms has been advanced by the identification of common and rare genetic variants associated with AF. Linkage analyses and candidate gene approaches have identified mutations in a variety of genes encoding cardiac ion channels, gap junction proteins, and signaling molecules. In contrast, genome-wide association studies (GWAS) have identified and validated 9 common AF susceptibility alleles, with several loci on chromosome (chr) 4q25 having the strongest association with AF (relative risk 1.39-1.72). Although the mechanism for this association remains uncertain, the locus is adjacent to the paired-like homeodomain transcription factor 2 (PITX2) gene which is critical for cardiac development, and reduced Pitx2 expression generates AF risk in mice. Given how commonly leaky RyR2 channels are found in studies of human AF, and that individuals carrying 4q25 risk alleles respond better to Class IC drugs flecainide and propafenone, both of which also inhibit RyR2 channels, this raises the hypothesis that PITX2 variants and possibly other rare AF-linked variants may initiate a cascade of cellular signaling events that ultimately leads to deranged RyR2 gating, which then contributes to AF by increasing Ca leak, generation of DADs and triggered activity. Hence, such derangement of Ca handling may constitute a common electrophysiological mechanism by which common genetic variants increase susceptibility to paroxysmal AF. To investigate this hypothesis, we will conduct a proof-of-concept clinical trial whereby the role of Ca leak for paroxysmal AF will be tested in humans by comparing AF suppression in the clinical EP laboratory. (R)- and (S)-propafenone have varying degrees of RyR2 channel inhibition and will therefore be used as tools to provide the first evaluation of whether RyR2 Ca leak contributes to AF inducibility in humans.

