0:45→0:55	Sterile Prep and Drape	
0:55→1:00	 Operator Scrubs Official Time-out 	Study Drug Infusion Starts (0:55)
1:00→1:10	Venous Sheaths Placed	Study Drug Infusion Ends (1:05)
1:10→1:20	CS Catheter Placed	
1:20→1:25		 Blood Sample Drawn + TEE EP Study (AVNERP, AERP) Rapid Atrial Pacing Protocol 1° Endpoint Determined End of Research Protocol
1:25→end	AF ablation proceeds according to standard of care procedures	

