- A standard electrophysiologic (EP) study will be performed at the start of the case after intracardiac catheter placement (including a decapolar CS catheter). The standard clinical EP study includes

measurement of AV block cycle length, AV node effective refractory period (ERP), atrial ERP, and ventricular block cycle length. Diastolic pacing threshold will be determined, and AERP will be tested at a pacing output of 2 times the diastolic threshold at 2 ms (standard of care). Following measurement of these conduction intervals, the pacing protocol to test for AF inducibility will be performed as follows:

- Stimulation Protocol #1:
 - A standardized protocol will be used to induce AF or atrial flutter (AFL).
 - This protocol is similar to common clinically used protocols to induce supraventricular tachyarrhythmias during performance of clinical EP studies.
 - The LA will be paced from the most distal CS electrode that can consistently capture the atrium. The CS catheter will be placed in standard clinical position.
 - o 15 beat bursts of 20mA amplitude and pulse width of 2 msec will be used
 - We will wait 10 seconds between bursts and decrement by 10msec for each burst
 - Step 1: starting cycle length will be 250 msec and decrement down to 180 msec or loss of 1:1 atrial capture (AERP). If there is no 1:1 capture at 250ms, the starting cycle length will be 10ms greater than the coupling interval of the atrial ERP at a drive train of 600 ms.
 - Step 2 will be used if there is no sustained AF/AFL during Step 1, and it will consist of 5 atrial pacing bursts of 15 seconds at the lowest cycle length of which 1:1 atrial capture was achieved.
 - The parameters for this AF induction pacing protocol can be programmed into the cardiac stimulator system (EP-4 Cardiac Stimulator, St. Jude Medical Inc., St. Paul, MN) and performed automatically. The time required to perform Step 1 of the research pacing protocol is ≤ 96 seconds, and Step 2 (conditional on step 1 being non-inducible) is ≤ 125 seconds.
 - Sustained AF/AFL will be defined by a duration of >30 seconds.
 - Patients who develop sustained AF/AFL will either: 1) spontaneously convert prior to ablation; 2) convert during the ablation procedure (majority of patients); or 3) undergo direct current cardioversion (DCCV) at the end of the case. DCCV during AF ablation procedures is common and will be performed according to standard clinical practice at the discretion of the attending physician.

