9.0 Study Withdrawal/Discontinuation

Participants may withdraw from the study at any time by informing the study staff verbally or in writing. If an individual withdraws their consent, we will withdraw the participant. Contact information for the PI and study staff will be made available to the participant upon enrollment in the consent document. Any remaining biological samples and data will be destroyed. Any data or biological samples that have been used for research prior to their withdrawal request will not be withdrawn and destroyed.

A participant may be withdrawn from the study by the PI if any of the following occurs:

- i. A procedural complication occurs prior to completion of the study protocol that requires the AF ablation procedure to be aborted, or precludes collection of study data.
- ii. The patient becomes hemodynamically unstable for any other reason that requires the AF ablation procedure to be cancelled prior to completion of the study protocol, or precludes the collection of study data
- iii. The primary operator determines it is in the patient's best interest to forego completion of the study protocol
- iv. The patient spontaneously converts to AF or atrial tachycardia/flutter prior to completion of study protocol

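### The primary analysis drops patients in whom only AFL was induced, which is a post-infusion result, and the protocol does not settle whether its target is AF or AF/AFL

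*Combined protocol and SAP*

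**What the plan says.** On the exclusion, Section 10 reads: "Patients who had only AFL induced will not be included in the primary analysis, but will be included in a secondary analysis". It does not describe that secondary analysis further.

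On the target, the sections differ:

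- **AF.** Section 1 presents the trial as the first evaluation of "whether RyR2 Ca leak contributes to AF inducibility in humans". The overarching aim in Section 2 is that "RyR2 blockade is beneficial for preventing AF induction in humans with paroxysmal AF". The hypothesis, endpoint and ordinal scale in Section 10 all refer to AF alone.
- **AF/AFL.** The Specific Aim in Section 2 is superiority of R over S "in suppressing induction of AF/AFL by a rapid atrial pacing protocol". Section 6 defines the sustained event as AF or AFL lasting more than 30 seconds. For AF/AFL arising during the clinical EP study it adds: "If it sustains >30 seconds it will be counted toward the primary endpoint, and the research AF induction pacing protocol will not be performed".

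Three other provisions bear on the point:

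- **Pacing sequence (Section 6).** "Step 2 will be used if there is no sustained AF/AFL during Step 1", so sustained AFL at Step 1 ends the pacing test.
- **Withdrawal (Section 9, item iv).** The investigator may withdraw a participant if "The patient spontaneously converts to AF or atrial tachycardia/flutter prior to completion of study protocol".
- **Timing (Section 5, Table 3).** The infusion ends at 1:05, and the EP study and pacing run from 1:20 to 1:25.

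Section 10 lists Stages 0, 1 and 2 but does not define Stage 0. It also does not say which stage an induction during the EP study receives.

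**The concern.** By Table 3, every AFL-only classification is made after the randomised drug has been given. Excluding these patients removes people who were randomised, infused and tested, because of what the test showed. The drug is studied for its effect on induced rhythm, so equal AFL-only frequency in the two arms cannot be presumed. If it differs, the arms compared are no longer the randomised arms.

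The unsettled target makes this worse. A patient whose only arrhythmia is sustained AFL in the EP study is a primary event under Section 6 and outside the primary analysis under Section 10. Both instructions cannot be followed. Depending on how the plan is read, the primary result could support or refute a claim about AF, or about AF/AFL, when that rhythm does not differ between arms.

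**Working it through.** **Inputs from the documents.** Section 10 gives 108 (R) + 108 (S) + 27 (placebo) = 243, and the sum agrees. The documents give no AF rate, AFL rate or significance level, so all rates below are assumptions and the test is taken as two-sided 5% (2.5% each way).

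**Algebra, free of assumed rates.** Let a = P(AF), f = P(AFL-only) and u = 1 − a − f = P(neither).

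- Rate after exclusion: a/(1−f).
- It equals a only if f = 0 or a = 0.
- Setting a/(1−f) = a+f gives f(1−a−f) = 0, so it equals a+f only if f = 0 or everyone is induced.
- The odds after exclusion are a/u, AF against neither. The R-to-S odds ratio is (a_R/u_R)/(a_S/u_S). It is well defined, but conditional on a post-infusion result.

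**Scenario (a): AF/AFL equal at 60%.** S has AF 50%, AFL-only 10%, neither 40%. R moves 5, 10 or 15 points from AF to AFL-only.

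- S: 0.50/0.90 = 55.6%.
- R: 0.45/0.85 = 52.9%; 0.40/0.80 = 50.0%; 0.35/0.75 = 46.7%.
- Odds ratios: 45/50 = 0.90; 40/50 = 0.80; 35/50 = 0.70. For AF/AFL the true value is 1.
- Expected exclusions out of 108: S 10.8; R 16.2, 21.6, 27.0.

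**Scenario (b): AF equal at 40%.** S has AFL-only 20%, neither 40%. R has AFL-only 15%, 10% or 5%.

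- S: 0.40/0.80 = 50.0%.
- R: 0.40/0.85 = 47.1%; 0.40/0.90 = 44.4%; 0.40/0.95 = 42.1%.
- Odds ratios: 40/45 = 0.89; 40/50 = 0.80; 40/55 = 0.73. For AF the true value is 1.
- Expected exclusions out of 108: S 21.6; R 16.2, 10.8, 5.4.

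**Simulation.** 400,000 trials, 108 per arm, pooled two-proportion test, unadjusted. Entries are the percentage of trials finding R superior (nominal 2.5%).

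| Handling of AFL-only | (a) 5 / 10 / 15 points | (b) 5 / 10 / 15 points |
|---|---|---|
| Dropped, as planned | 5.6 / 11.4 / 22.1 | 5.9 / 11.4 / 19.2 |
| Counted as induced | 2.4–2.5 | 10.7 / 30.7 / 59.4 |
| Coded as not AF | 10.8 / 30.8 / 60.2 | 2.4–2.5 |

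Each coding holds its level only for its own target, and dropping holds it for neither. With the arms swapped at the largest shift, dropping finds S superior in 21.9% (a) and 19.2% (b). With no drug effect on either rhythm (45/15/40 in both arms), dropping gives 2.5% each way.

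**Ordinal check.** 200,000 trials, tie-corrected rank test on Step 1 / Step 2 / not induced, with 40%, 60% or 80% of inductions at Step 1. Stage 0 is taken as not induced, and EP-study inductions are not modelled. Dropping gives 5.1–5.3%, 10.4–10.8% and 19.7–20.3% in (a), and 5.6%, 10.6–11.0% and 17.9–18.2% in (b). The matching coding gives 2.5%.

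**Other rates.** Take S at AF 40%, AFL-only 10%, neither 50%. A normal approximation then gives two-sided rejection of 15.8% for a 10-point AF-to-AFL shift under R (AF/AFL equal). For a 10-point move from neither to AFL-only (AF equal) it gives 11.7%, now tending to favour S. The nominal figure is 5%.

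Covariate adjustment, item iv withdrawals and the placebo arm are not modelled.

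**The case against.** **No error arises without a real drug effect on some rhythm.** In (a) R does lower AF, which is Section 10's own hypothesis. In (b) R does lower AF/AFL, which is the Specific Aim. If the drug does nothing, the level holds. This stands: the harm is a claim attached to the wrong rhythm, or a distorted estimate, not invented drug activity.

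**The magnitudes are assumed.** The largest figures need AFL-only to differ by 15 points between enantiomers; at 5 points they are 5.6% and 5.9%. This also stands. It limits what can be said about size and direction, but not the algebra.

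**Coding AFL-only as not AF is imperfect.** Sustained AFL at Step 1 means AF at Step 2 is never sought. Suppose AF would be induced with probability 25% at each step, so 1 − 0.75² = 43.75% over two steps, and AFL pre-empts it with per-step probability q. Observed AF is 0.25(1−q)[1 + 0.75(1−q)], and the probability of neither is [0.75(1−q)]². With q = 6% under S and 12% under R:

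- Observed AF is 40.1% v 36.5%, which favours R.
- AFL-only is 10.2% v 19.9%, so dropping gives 0.401/0.898 = 44.6% v 0.365/0.801 = 45.6%, which favours S.

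Neither recovers underlying AF inducibility. An AF target therefore has to be stated as AF induced under this protocol, with that limit declared.

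**The data are kept in a secondary analysis.** True, but that analysis is undefined and the trial's claim rests on the primary.

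**Item iv may apply only before the infusion.** The text gives no timing, so a second post-infusion exclusion is possible rather than shown.

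**Conclusion.** The concern holds, and the rule is wrong as written. The structural part needs no assumed rates: the primary set is selected on a post-infusion result, and what it estimates is neither of the two targets the protocol names. The contradiction between Sections 6 and 10 over sustained AFL in the EP study is plain on the page.

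The size is not known. For differences of 5 to 15 points in AFL-only at 108 per arm, the chance of a wrong superiority claim for the named target rises from 2.5% to between about 5.6% and 22.1%, in either direction. That range rests on the assumed rates and an unadjusted test. With no drug effect on either rhythm, the only cost is lost patients. Undefined Stage 0 and item iv are smaller clarifications that belong in the same amendment.

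**What to change.** 1. Delete the exclusion sentence in Section 10.
2. Name one target, AF or AF/AFL, and reconcile Section 2, Section 6, Section 9 item iv and Section 10 to it.
3. Keep every randomised, infused and tested patient in the primary analysis, and state that testing includes the clinical EP study. For AF/AFL, AFL-only takes the stage at which it was induced. For AF induced under this protocol, AFL-only is not induced, with a note that pacing stops after sustained AFL and later AF is unobserved.
4. Define Stage 0, and state the stage given to inductions during the EP study.
5. State how AF or flutter that begins after the infusion but before protocol completion is counted.
6. Report by arm the AFL-only counts (also by stage) and the item iv withdrawals. Give the other coding as a sensitivity analysis.

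**Cost.** No new patients or data. An AF target changes the exclusion sentence and the AF/AFL wording in Sections 2 and 6. An AF/AFL target also changes the hypothesis, endpoint and ordinal sentences in Section 10. Stage 0 and item iv need a line each.

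The real cost is timing. Section 10 reports that a treatment comparison on the new ordinal endpoint (P = 0.075) was reviewed in March 2019, and does not say how AFL-only patients were handled in it. The amendment should therefore be dated and made by people without arm-level results. The analysis as Section 10 now states it should be reported alongside the corrected one.
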